**Study Duration:**

This is a 5-year study. Eligible participants will be enrolled throughout the duration of the study. It is anticipated that study enrollment goal will be met six months prior to study ending in year 5. Individual participant's participation will approximately be 11 weeks from time of enrollment into the study. We anticipate the completion of all study procedures, including data analysis and results to report, will take approximately a year once the study has completed all data collection from study participants.

**Use of radiation: N/A**

**Use of Center for Magnetic Resonance Research:**

All participants who consent to MRI testing will get a 3T structural and functional MRI scan at Visit 2 and after completion of the 7-week treatment course (Visit 3). They will use the changing room to change into scrubs according to the CMRR protocol.

## **6.0 Data and Specimen Banking**

### **6.1 Storage and Access:**

All data used for this project will be obtained after receiving informed consent from all participants. The research material collected in this project are in the form of: (1) magnetic resonance imaging (MRI) records, (2) standardized patient-rated questionnaires, clinical assessments, and (3) blood serum.

Clinical data will be stored on Research Electronic Data Capture (REDCap), physical paper files will be kept in a locked file drawer in the study coordinator's office, and on encrypted servers (Box). Participant confidentiality will be safeguarded by the use of password protected databases and locked file cabinets. Research records will be stripped of all identifying information, with keys identifying individual participants available only to the PI or selected designees. Further, access to identifiable private information from study participants will only be accessible to study-related personnel who have met the training requirements for the responsible conduct of research, Good Clinical Practice, HIPAA, and data security, and who have completed all initial and annual study specific training.

Blood samples will be collected at each enrolling site and stored locally in a -80 freezer at UMN. Blood samples will be labeled by ID number, type (plasma or serum), and date of draw. A password-protected tracking sheet will be used to link participants' blood samples with identifiable information

(i.e., date of birth). This sheet will only be accessed by the IRB-approved study staff.

At the baseline and final evaluation, we will draw 38 ml of blood (20 mL plasma, 18 mL serum) after an overnight fast and store it at -80° Celsius until batch processing in the lab of the PI.

#### 6.2 Data:

All clinical assessments and standardized patient-rated questionnaires will be stored on Research Electronic Data Capture (REDCap) and on encrypted servers.

Imaging of brain activation and connectivity (resting-state and task-based fMRI), will be preprocessed using the HCP preprocessing pipeline. MRI data will be stored in digital form on encrypted servers.

We will bank blood serum and plasma for long-term storage. To minimize the risk of loss of privacy all records will be kept confidential and identified by study code only in the working databases. Blood samples will be stored without identifiers using only the study code.

#### 6.3 Release/Sharing:

The results will be submitted for publication in scientific journals and presented at conferences. In case the scientific journals request the original database, the de-identified Excel file with scoring and codes will be shared on their protected databases.

### 7.0 Sharing of Results with Participants

#### 7.1 Sharing Results:

No information will be provided to the participant unless the information indicates that the participant may be at risk for a serious illness known at the time of testing to be treatable. In that case, the study doctor will attempt to notify the participant. The research participant and their clinical care person(s) are responsible for further evaluation/follow-up in response to MRI incidental findings. Participants will be given the option to opt out of receiving any incidental findings.

#### 7.2 Sharing Genetic Results: N/A

##### 7.2.1 Disclosure of Results: N/A

##### 7.2.2 Returning Results to Participants: N/A

Aggregate or individual results: N/A

Laboratory results: N/A

Plan for return of results to participants: N/A

Types of results to be returned to participants: N/A

7.2.3 Future analysis of genotypes: Future genome sequencing may be conducted but will not be used for clinical diagnosis and will not have any clinical utility.

## 8.0 Study Population

Inclusion Criteria:

- 18 years of age or older
- Injured for  $\geq 3$  months
- Completed inpatient rehabilitation and living in the community
- Chronic sublesional neuropathic pain defined as persistent pain (VAS grade 3-10) for three months or more
- For people of child-bearing potential: currently practicing an effective form of two types of birth control (defined as those, alone or in combination, that result in a low failure rate (i.e., less than 1% per year) when used consistently and correctly).

Exclusion Criteria:

- Progressive myelopathy secondary to posttraumatic cord tethering or syringomyelia
- Active use of drugs known to interact with brivaracetam: rifampin, carbamazepine, sodium oxybate, buprenorphine, propoxyphene, levetiracetam, and phenytoin.
- Brain injury or cognitive impairment limiting the ability to follow directions or provide informed consent
- Pregnancy or lactation
- Epilepsy or active treatment for seizure disorder
- Past or current suicidality
- Active treatment for psychiatric disease
- Drug addiction
- Moderate or heavy alcohol intake (up to four alcoholic drinks for men and three for women in any single day, and a maximum of 14 drinks for men and 7 drinks for women per week)

- Hepatic cirrhosis, Child-Pugh grades A, B, and C
- Impaired renal function (GFR<60ml/minute)
- Contraindications to brivaracetam or pyrrolidine derivatives including allergy
- Active clinically significant disease (e.g., renal, hepatic, neurological, cardiovascular, pulmonary, endocrine, psychiatric, hematologic, urologic, or other acute or chronic illness) that, in the opinion of the investigator, would make the patient an unsuitable candidate for this trial.
- History of malabsorption or other gastrointestinal (GI) disease that may significantly alter the absorption of brivaracetam
- Use of any investigational drug 30 days prior to enrollment in this study
- Dependent on mechanical ventilation.
- Use a gastrostomy tube (G-Tube) for feeding.
- Enrollment in another clinical trial.

People with contraindications to MRI including retained bullet fragments, noncompatible metal implants, and implanted devices such as non-MRI compatible baclofen pumps may still be eligible for the study; they will not participate in the MRI scans.

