*International Spinal Cord Injury Pain Data Set.* This tool assesses average pain intensity in the last week using a 0-10 numerical rating scale. The 0-10 numerical rating scale has been recommended by the IMMPACT consensus group for use in pain clinical trials [Dworkin et al., 2005] and by the 2006 NIDRR SCI Pain outcome measures consensus group. [Bryce et al., 2007] This scale is recommended to standardize pain outcomes across studies. The International Spinal Cord Injury Pain Data Set also assesses dimensions of pain (i.e., intensity of pain, time of day, location, occurrence, etc.), and pain interference with mood, activity, and sleep.

*Modified Brief Pain Inventory (BPI).* The BPI is a short self-assessment questionnaire that provides information on various dimensions of pain including how pain developed, the types of pain a patient experiences, and time of day pain is experienced, as well as current ways of alleviating pain [Cleeland and Ryan, 1994]. The BPI also consists of the numeric pain rating scale, a simple 10-point scale (0 = “no pain”, 10 = “pain as bad as you can imagine”) measuring a patient’s worst pain and least pain, on average in the last 24h and at present time. The Brief Pain Inventory provides information on the intensity of pain (the sensory dimension) as well as the degree to which pain interferes with function (the reactive dimension). According to several previous studies on pain in spinal cord injury, the BPI is an effective measure [Bryce et al., 2007].

*DN4 Assessment Tool.* This is a 4-item assessment that characterizes neuropathic pain.

*Assessment of Mood with the Patient Health Questionnaire (PHQ-9).* This is a 9-item scale that assesses patient quality of life through mental state. It identifies active suicidality [Kroenke et al., 2001]. It assists physicians in both diagnosing depression and determining a treatment route. It incorporates DSM-IV depression classifications and determines severity of depression [Bombardier et al., 2004; Graves and Bombardier, 2008; Kalpakjian et al., 2009; Krause et al., 2010].

*Satisfaction with Life Scale (SWLS).* This is a 5-item scale that assesses patient happiness with current quality of life [Diener et al., 1985]. It consists of a 1-7 Likert scale.

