
*Intervention Expectations.* This self-report will assess what participants expect their outcomes to be during and after their participation in the study.

*Study Expectancies.* Participants respond to 24 items about how they think they will function 7 weeks from now in areas such as pain, sleep, participation, work, social activities, and sexual functioning.

*Concurrent Pain Medication Use.* Although pain medications can confound the analgesic effects of brivaracetam, we consider it to be unethical to require participants to discontinue pharmacologic treatment for pain over the course of the study as a criterion for enrollment. In addition, to increase generalizability, it is important to recruit participants using pain medications. Therefore, we will record pain medication use over the course of the trial and consider this in the analysis.

*Pain Intensity and Medication Use Diary.* We will monitor daily pain reports and patient medication throughout the course of the study using a Pain Intensity and Medication Use Diary. Participants will be asked to record daily pain ratings (highest pain 0-10, lowest pain 0-10, and average pain 0-10) and any pain medication use. This diary will be started 1 week prior to drug treatment and maintained until completion of the study.

*Assessment of Brain Function with MRI.* All scans will be performed on the same scanner for this study. We will use the Siemens 3-T Prisma multi-band scanner. Prior to each scan, participants will be asked five questions regarding their pain now and over the last week as well as alcohol, caffeine, and tobacco use over the past 12 hours.

1. Structural MRI acquisition: We will acquire a T1-weighted Magnetization-Prepared Rapid Acquisition with Gradient Echo (MPRAGE) image [Repetition Time (TR)=2.5s, Echo Time (TE)=4.5ms, 0.8mm^3 voxels], and a T2 weighted Sampling Perfection with Application optimized Contrasts using different flip angle Evolution (SPACE) image [TR=3.2s, TE=565ms, 0.8mm^3 voxels]. We use special sequences for the scans to reduce the impact of head motion.

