#### Screening:

A phone screen will be administered to confirm basic eligibility criteria listed in Section 8.1 such as age, pain level, medication use, and other medical conditions. For those that agree to have an MRI, we will screen participants for contra-indications for MRI compatibility with the CMRR pre-screening questionnaire. If participant meets basic eligibility requirements, we will request that they obtain medical clearance for study participation from their primary care provider or other medical professional, including collecting 3-4 tablespoons of blood for screening blood work (described in detail below) and completing a physical exam and health history. This must be conducted within 1 month (or up to 6-weeks) of Visit 1. The participant's insurance will be charged, and they will be responsible for any associated copays or costs.

The participant's provider will send research staff the results via fax or email, or the participant may carry a hard copy to Visit 1. If a patient is part of the enrolling site's system of care, their medical records will be accessed directly by research staff who have obtained the appropriate approvals (e.g., NERS approval).

*Screening bloodwork for hepatic cirrhosis, renal insufficiency, and pregnancy.* Brivaracetam treatment is not safe for those who are pregnant, have hepatic cirrhosis, or kidney dysfunction. Therefore, to be medically cleared to enter the study, participants must complete a fasting blood draw through their primary care clinic for analysis of blood urea nitrogen (BUN), creatinine, alanine transaminase (ALT), aspartate transaminase (AST), total bilirubin, albumin, GFR, calcium, corrected calcium, and human chorionic gonadotropin (hCG); urine hCG test will also be accepted. International normalized ratio (INR) will be collected at the discretion of the participant's primary care provider if the participant is on anticoagulation or has abnormal liver function tests. People who are menopausal and have not had a menstrual period for at least 12 months, or people who have had a hysterectomy will not be required to take pregnancy tests. We will use lab work performed clinically during any recent visit (within one month or up to 6-weeks of testing) for screening labs when available. Any participant found to have renal insufficiency (GFR<60ml/minute), hepatic cirrhosis, Child-Pugh grades A, B, and C, or pregnant (positive hCG) will be considered a screen fail and will not progress in the study.

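### No entry criterion requires background pain medication to be unchanged before Visit 1, so the primary change score can start from an unsettled baseline

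*Combined protocol and SAP*

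**What the plan says.** The eligibility list in section 8.0 restricts other medication by two entries. One is "Active use of drugs known to interact with brivaracetam: rifampin, carbamazepine, sodium oxybate, buprenorphine, propoxyphene, levetiracetam, and phenytoin", which carries no time window. The other is "Use of any investigational drug 30 days prior to enrollment in this study", the only drug look-back in the list. The pain criterion is "Chronic sublesional neuropathic pain defined as persistent pain (VAS grade 3-10) for three months or more", which concerns how long pain has lasted and how severe it is, not whether its treatment has been stable.

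Screening, described in sections 5.0 and 8.0, is a phone call covering "basic eligibility criteria listed in Section 8.1 such as age, pain level, medication use, and other medical conditions". It sets no window and no stability test.

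Section 5.0 permits background analgesics. It holds that requiring people to stop them would be unethical and that, for generalisability, "it is important to recruit participants using pain medications". Its remedy for confounding is that "we will record pain medication use over the course of the trial and consider this in the analysis". Of the daily pain and medication diary it says: "This diary will be started 1 week prior to drug treatment and maintained until completion of the study".

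The primary measure is the International SCI Pain Data Set: "This tool assesses average pain intensity in the last week using a 0-10 numerical rating scale". Table 1 places the surveys at Visits 1, 3 and 4, so the baseline rating is taken at Visit 1. Section 15.2 powers the trial on the between-arm difference in pre-post change. The covariates that section 15.1 gives as examples are demographics, SCI severity and time since injury; pain medication is not among them.

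**The concern.** A pre-post change score assumes that the starting rating describes a settled state. If an analgesic was started, stopped or changed in dose shortly before Visit 1, the last-week rating falls partly or wholly within that change. The rating taken about five weeks later then differs for reasons unrelated to study drug. With about 20 completers per arm and simple 1:1 allocation, extra variance in the change score is costly.

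The existing safeguards do not reach this case. Three months of pain can coexist with a regimen altered last week. The phone screen asks about use, not about recent change. Participants appear to receive the diary only once randomised, so it should not cover the week recalled at Visit 1. Recording medication during the trial cannot recover a change made before it began.

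**Working it through.** **Is the gap closed elsewhere?**

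| Place | What it covers | Keeps out or identifies a recent analgesic change? |
|---|---|---|
| 8.0, interacting drugs | Current use of seven named drugs | No |
| 8.0, investigational drugs | 30-day look-back | No; investigational drugs only |
| 8.0, pain criterion | Duration and severity of pain | No |
| 5.0 and 8.0, phone screen | Medication use | No window or stability rule |
| 5.0, diary | From 1 week before drug | Not the Visit 1 recall week, if issued after randomisation |
| 5.0, concurrent medication | Use over the course of the trial | No |
| 15.1, covariates | Demographics, severity, time since injury | Pain medication not named |

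Nothing closes the gap.

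**Inputs for an illustration of size.** From section 15.2: difference 2 points, 20 per arm, two-sided 5%, stated power above 80%, and a pain-score SD of 3.17 (28 adults). Not in the documents and therefore assumed: a share f of 10% to 30% of entrants with a recent change, and a drift m of 1 to 2 points in those people, the same in both arms.

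**The plan's own figure first.** Power comes from the two-sample t-test (noncentral t, 38 degrees of freedom), with noncentrality 2 / (SD × √(2/20)).

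- With SD = 3.17 used as the SD of change, power is 49.4%, so the stated figure is not reproduced. The quoted SD is that of a pain score; the SD of change is not given.
- Solving for 80% power gives a change SD of 2.20.

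Both are carried forward as starting points.

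**Added variance.** If a share f drifts by m regardless of arm, the variance of the change score rises by f(1 − f)m².

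- Smallest case, f = 0.1, m = 1: 0.1 × 0.9 × 1 = 0.09.
- Largest case, f = 0.3, m = 2: 0.3 × 0.7 × 4 = 0.84.

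| Starting SD | Case | New SD | Power at 20 per arm |
|---|---|---|---|
| 2.20 | none | 2.20 | 80.0% |
| 2.20 | smallest | √(4.84 + 0.09) = 2.22 | 79.3% |
| 2.20 | largest | √(4.84 + 0.84) = 2.38 | 73.4% |
| 3.17 | none | 3.17 | 49.4% |
| 3.17 | smallest | √(10.05 + 0.09) = 3.18 | 49.0% |
| 3.17 | largest | √(10.05 + 0.84) = 3.30 | 46.3% |

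The loss is roughly 0.7 to 6.6 percentage points from a start of 2.20, and from under half a point to 3 points from a start of 3.17.

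**The case against.** **Broad entry is a reasoned choice in a pilot.** Section 5.0 argues for enrolling people who use pain medication, and the protocol calls the study a pilot. That stands as a reason not to demand that anyone stop treatment. It is not an argument against asking that a continuing regimen be unchanged for a period before baseline.

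**The size is assumption on assumption.** This stands. The share and the drift are assumed, and the SD of 2.20 is back-solved. Adding variance to either SD also presumes that it contains none of this noise already, and the documents do not say whether the source sample had stable regimens. At the low end the loss is negligible.

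**The remedy is partial.** This also stands. Analgesic changes during treatment remain possible and are only recorded.

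**Stronger readings that a reader might infer:**

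- *That people who have just stopped a listed interacting drug enter with it still in their system.* The documents give no clearance information for any of the seven drugs. Provider clearance and the contraindication exclusion also apply, and drug is dispensed at Visit 2. What can be said is that the current-use wording is undefined in time. A washout for those drugs would be a clinical rule and is not proposed here.
- *That the treatment comparison is biased.* Recent changes before randomisation fall on both arms alike in expectation.
- *That chance imbalance between arms is a further harm.* It is already in the standard error of the comparison, so it should not be counted on top of the power loss.

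**Conclusion.** The point holds as a low-cost design improvement. Section 8.0 does not require stable pain medication before Visit 1, and no other part of the protocol screens out or identifies a recent change before the baseline rating. The consequence is added noise in the primary change score, not systematic bias.

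Its size cannot be computed from the documents. Under the assumed 10% to 30% of entrants and 1 to 2 points of drift, the power loss ranges from under 1 percentage point to about 7. The upper end needs both the largest assumed values and a change SD of 2.20; with 3.17 the largest loss is about 3 points. The gap between the stated power and the quoted SD is a separate matter and does not affect this conclusion.

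**What to change.** In section 8.0, add an entry criterion that no pain medication was started, stopped or changed in dose during a fixed period before Visit 1. The sponsor should choose and justify the period; the 30-day look-back already used for investigational drugs is one precedent within the list. State that current regimens continue and that candidates who do not meet the criterion are deferred, not rejected.

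Ask the question at the phone screen, before labs are drawn. Record the date of the last pain-medication change in the Visit 1 health history.

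Separately, the sponsor should clarify what current use means in time for the listed interacting drugs.

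The cost is one eligibility line, one screening question, one dated field, and a wait for some candidates. If a change comes to light only at Visit 1, safety labs or medical clearance may need repeating. With a 30-day deferral, labs stay inside the 6-week limit only if they are no more than 42 − 30 = 12 days old at that point. Table 1 footnote a gives one month for medical clearance, although the screening text in section 8.0 allows up to 6 weeks; those two statements should be reconciled.

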#### Screening:

A phone screen will be administered to confirm basic eligibility criteria listed in Section 8.1 such as age, pain level, medication use, and other medical conditions. For those that agree to have an MRI, we will screen participants for contra-indications for MRI compatibility with the CMRR pre-screening questionnaire. If participant meets basic eligibility requirements, we will request that they obtain medical clearance for study participation from their primary care provider or other medical professional, including collecting 3-4 tablespoons of blood for screening blood work (described in detail below) and completing a physical exam and health history. This must be conducted within 1 month (or up to 6-weeks) of Visit 1. The participant's insurance will be charged, and they will be responsible for any associated copays or costs.

The participant's provider will send research staff the results via fax or email, or the participant may carry a hard copy to Visit 1. If a patient is part of the enrolling site's system of care, their medical records will be accessed directly by research staff who have obtained the appropriate approvals (e.g., NERS approval).

*Screening bloodwork for hepatic cirrhosis, renal insufficiency, and pregnancy.* Brivaracetam treatment is not safe for those who are pregnant, have hepatic cirrhosis, or kidney dysfunction. Therefore, to be medically cleared to enter the study, participants must complete a fasting blood draw through their primary care clinic for analysis of blood urea nitrogen (BUN), creatinine, alanine transaminase (ALT), aspartate transaminase (AST), total bilirubin, albumin, GFR, calcium, corrected calcium, and human chorionic gonadotropin (hCG); urine hCG test will also be accepted. International normalized ratio (INR) will be collected at the discretion of the participant's primary care provider if the participant is on anticoagulation or has abnormal liver function tests. People who are menopausal and have not had a menstrual period for at least 12 months, or people who have had a hysterectomy will not be required to take pregnancy tests. We will use lab work performed clinically during any recent visit (within one month or up to 6-weeks of testing) for screening labs when available. Any participant found to have renal insufficiency (GFR<60ml/minute), hepatic cirrhosis, Child-Pugh grades A, B, and C, or pregnant (positive hCG) will be considered a screen fail and will not progress in the study.

